7.0 Study Procedures

In the study, patients will be randomized to one of two groups. Arm 1 will be participants who receive intraperitoneal bupivacaine and arm 2 will be participants who receive placebo (saline).

All patients involved in the study will be undergoing pelvic organ prolapse surgery with peritoneal access and will receive either 30 mL of 0.25% Bupivacaine or 30 mL of saline by means of intraperitoneal lavage. This will be performed at which point peritoneal access will no longer be available, and the solution will be left in the abdomen upon completion of the procedure.

Preoperatively, patients will receive a standardized pain control regimen of Ibuprofen and Tylenol in accordance with hospital ERAS protocol. Postoperatively, patients will receive standardized pain control regimen of Ibuprofen and Tylenol in accordance with hospital ERAS protocol. Patients can be given as needed narcotics if pain is poorly controlled on the initial regimen.

All patients will have pain scores measured at approximately 4 hours using a NRS following completion of the procedure. All patient will have pain scores measured at approximately 8, 12 and 24 hours by means of text message NRS (in the event of same day surgery discharge) vs inpatient in person NRS (for planned admission), following completion of the procedure, which will be stored directly into REDCap. Time to first narcotic dose will be obtained through the hospital electronic medical record. Hospital length of stay will be obtained through the hospital electronic medical record.

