12.0 Statistical Considerations

Sample size/Power

This is a double-blind randomized controlled study to compare two techniques of pain management strategies for woman undergoing advance-organ prolapse surgery with the primary outcome being the numeric rate scale (NRS) at 4 hours post-surgery. Secondary outcomes will be the NRS collected at 8, 12, and 24 hours, and an indicator of whether woman required opioids (Y/N) within 4 hours of surgery.

Assuming a SD = 2.14^2 in the NRS at 4 hours, to detect a meaningful change of 1.3 would be an ES = 0.60 (1.3/2.14). To have 80% power to detect an effect size of this magnitude (i.e., a 0.6 SD difference in the NRS between treatment arms) based on a two-sided two-sample independent t-test with type I error set at 0.05 requires a total sample size of N = 90 (45 per group). As we expect no attrition or missing data on the primary outcome, N = 90 will be our planned sample size.

Randomization

Patients will be randomized 1:1 to the two pain strategies using stratified randomization with surgery technique being the strata. Block randomization will be used with blocks of size 4. Randomization lists will be constructed by the study statistician using statistical software.

Statistical Methods

Descriptive statistics of N, mean, standard deviation, median, minimum, and maximum or frequency and percent will be provided for all baseline characteristics overall and by treatment arm. Baseline characteristics which will be reported include surgical procedure (uterosacral ligament suspension vs sacrocolpopexy), age, BMI, menopausal status, surgical time, and intraoperative complications. Intraoperative complication will be a dichotomous variable of whether any complication occurred (Y/N). Baseline characteristics will be compared between the two study arms to verify randomization achieved balanced groups. Any characteristics that significantly differ will be considered in subsequent analyses.

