Assuming baseline characteristics are balanced between the two study arms, we will use a linear mixed model fit to all timepoints (4, 8, 12, and 24 hours) with effects of surgery technique, treatment group, time, and the time x treatment group interaction to estimate the mean difference in treatment groups at each time point. All model assumptions will be checked for adequacy. The mean difference and 95% confidence interval at each time point will be reported. A p-value of 0.017 will be used to indicate statistical significance in the NRS collected at the three other time points (8, 12, and 24) to maintain familywise type I error at .05. For

Version Date: 05/25/2023 Page 10 of 13

the dichotomous outcome of whether patients required opioids in the first 4 hours following surgery, a Fisher's exact test will be used.

Other outcomes can only be assessed among those that required opioids thus will have lower power. Thus, caution will be used in interpretation of results. These include the amount of MME in the first four hours and time to first dose. Descriptive statistics by study group will be estimated. For outcomes which may be normal, then a linear regression model will be fit with effect of surgery technique and treatment, to estimate the mean difference in the outcome by treatment and associated 95% confidence interval. If any outcome is non-normal, then a generalized linear regression model will be used instead with an appropriate distribution and link function to detect the effect of treatment.

- 1. Cohen J. Statistical power analysis for the behavioral sciences. L. Erlbaum Associates; 1988.

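### The mixed model holds the surgery-technique effect constant from 4 to 24 hours, so the reported 4-hour standard error can be slightly larger than necessary

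*Combined protocol and SAP*

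**What the plan says.** The primary outcome is the NRS pain score at 4 hours (Sections 2.1, 3.1 and 12.0). Patients are allocated 1:1 in blocks of 4, with "stratified randomization with surgery technique being the strata" (Section 12.0, Randomization; Section 6.0 agrees).

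Under Statistical Methods, the treatment difference at each time comes from one linear mixed model for all four times, containing "effects of surgery technique, treatment group, time, and the time x treatment group interaction". No time by technique term is listed and no covariance structure is named. The list of baseline characteristics gives the procedure two levels: "surgical procedure (uterosacral ligament suspension vs sacrocolpopexy), age, BMI, menopausal status, surgical time, and intraoperative complications". I take this two-level variable to be the technique stratum.

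The sample size was set separately, with a "two-sided two-sample independent t-test with type I error set at 0.05" and no adjustment for technique.

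**The concern.** The model treats its two between-patient factors differently. Treatment has its own effect at each time, while technique has one coefficient that serves as a weighted average over 4 to 24 hours. The primary question concerns 4 hours only. If the technique gap at 4 hours differs from that average, the 4-hour scores are adjusted by the wrong amount and the remainder is counted as noise.

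What is at stake is the width of the 4-hour confidence interval, not its centre. Stratified blocks keep the arms balanced on technique, so a poorly fitted technique effect cancels out of the treatment contrast. The point is worth raising because holding the technique effect constant gains essentially nothing for the 4-hour contrast, and relaxing it is nearly free.

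**Working it through.** **1. The plan's own figure.** Inputs from Section 12.0: two-sided 5% t-test; "To have 80% power to detect an effect size of this magnitude"; and "to detect a meaningful change of 1.3 would be an ES = 0.60 (1.3/2.14"). The exponent in "Assuming a SD = 2.14^2 in the NRS at 4 hours" reads as the marker for that section's reference 2, because the effect size divides by 2.14. Taken literally it would need about 196 per arm. With the noncentral t distribution, an effect size of 0.60 needs 44.59 per arm, rounded up to 45, so N = 90 is reproduced. Recomputed power at 45 per arm is 80.4% at 0.60 and 81.3% at 1.3/2.14 = 0.607.

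Reference precision at 4 hours: SE = 2.14 × √(2/45) = 0.451. The 95% half-width is 1.987 × 0.451 = 0.897 NRS points.

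**2. Excess SE from a constant technique effect.** Let g₄ be the technique gap at 4 hours, ḡ the pooled gap that the model fits, and p the share of one technique. With an unstructured covariance the 4-hour residual variance rises by p(1−p)(g₄−ḡ)², so

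SE ratio = √[1 + p(1−p)(g₄−ḡ)² / 2.14²].

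With a random intercept, one variance serves all four times, so (g₄−ḡ)² is replaced by the mean of (gₜ−ḡ)² over the four times.

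Assumptions, none from the documents: p = 0.5; SD 2.14 within technique; equal variances and correlations across times, which makes ḡ the simple mean; and the gap patterns below.

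| Technique gap at 4, 8, 12, 24 h | ḡ | g₄−ḡ | Excess SE, unstructured | Excess SE, random intercept |
|---|---|---|---|---|
| 0.5, 0.5, 0.5, 0.5 | 0.5 | 0 | 0% | 0% |
| 1, 0.5, 0.25, 0 | 0.4375 | 0.5625 | 0.9% | 0.4% |
| 1.5, 0.75, 0.375, 0 | 0.656 | 0.844 | 1.9% | 0.8% |
| 1.5, 0, 0, 0 | 0.375 | 1.125 | 3.4% | 1.1% |
| 2, 1, 0.5, 0 | 0.875 | 1.125 | 3.4% | 1.5% |
| 2, 0, 0, 0 | 0.5 | 1.5 | 6.0% | 2.0% |
| 1, 0, −0.5, −1 | −0.125 | 1.125 | 3.4% | 1.5% |

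Fifth row in full: 0.25 × 1.125² = 0.316; 0.316/4.580 = 0.0691; √1.0691 = 1.034. With a 70:30 mix the unstructured figures are smaller: 0.7% for the second row and 5.0% for the sixth.

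**3. Simulation check** (3000 trials per scenario, stratified blocks of 4, 90 patients, true difference −1.3, same SD convention).

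- Pattern 1, 0.5, 0.25, 0: mean half-width 0.902 as planned and 0.891 with time by technique.
- Pattern 2, 1, 0.5, 0: half-width 0.927 against 0.893. The mean reported SE is 0.466 against 0.449, but the actual spread of the estimate is 0.455 against 0.454. The mean estimate is −1.292 in both models, and coverage is 95.4% as planned.

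So the estimate is practically the same under either model. Only the reported SE differs.

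**4. Does this threaten the 80% power?** In step 3 the second pattern gives 78.5% power as planned and 80.6% with the extra term. That scenario puts the technique gap on top of 2.14: the total 4-hour SD is √(4.580 + 1) = 2.36, more than the plan assumes. An unadjusted t-test uses the total SD, so the fair comparison sets the total SD to 2.14. The planned model's 4-hour residual variance is then 2.14² − p(1−p)g₄² + p(1−p)(g₄−ḡ)², keeping ḡ as the simple mean.

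- 1-point fading gap: 4.580 − 0.250 + 0.079 = 4.409; SE = √(4.409 × 2/45) = 0.443, below the design value of 0.451.
- 2-point fading gap: 4.580 − 1 + 0.316 = 3.896; SE 0.416.
- Reversing gap (last row): 4.580 − 0.250 + 0.316 = 4.646; SE 0.454, which is 0.7% above design. Power for 1.3 points is 80.8% by formula and 80.2% in simulation.

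The planned model meets its target in all three.

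**The case against.** The strongest reply is that the plan already does what matters: it stratifies on technique and puts technique in the model. The estimate is unbiased, coverage is close to nominal, and under mild assumptions the loss is 1% or less. The larger figures need a technique gap of 1.5 to 2 points, or one that changes sign, and most of them also need an unstructured covariance, which the plan does not specify. All of that stands. The plan also says model assumptions will be checked, and a constant technique effect is one of them. That helps less, because no remedy is named and a term added after seeing the data is weaker than a prespecified one.

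A reader might go further in three ways that the documents do not support.

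- **That the plan itself gives a reason for the technique gap to change.** Section 7.0 scores patients after 4 hours by "text message NRS (in the event of same day surgery discharge) vs inpatient in person NRS (for planned admission"), but it does not link technique to same-day discharge, or scoring mode to score. A changing gap is an assumption.
- **That the trial is underpowered.** The sample size rests on an unadjusted test with SD 2.14, and step 4 shows no material shortfall.
- **That concomitant hysterectomy should also be a covariate.** The covariate lists in Sections 5.0 and 12.0 do not name it. But nothing says that it is done in this trial, how often, or that it affects 4-hour pain; hysterectomy appears only in background and cited literature. Section 5.0 also collects the type of procedure under an open-ended list.

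**Conclusion.** The point holds as a minor matter of precision. The model allows the treatment effect, but not the effect of the stratification factor, to vary over time. If the technique gap does vary, the reported 4-hour SE is slightly too large: about 0.4 to 1% for a 1-point gap that fades, and about 1 to 6% for gaps of 1.5 to 2 points that fade or occur only at 4 hours. If the gap is constant, nothing is lost. On the reference half-width of 0.897, 1% is 0.009 and 6% is 0.054 NRS points, against a target difference of 1.3.

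These sizes rest on an assumed technique mix, assumed gap patterns and the choice of covariance structure. The direction rests only on the model as written. There is no bias, no inflation of type I error and no damage to the stated power.

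**What to change.** In Section 12.0, Statistical Methods, list the fixed effects as: surgery technique (as randomised), time (categorical), treatment, time by treatment, and time by surgery technique. The 4-hour treatment contrast is then adjusted for the 4-hour technique difference.

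With two techniques and four times, the cost is (2−1) × (4−1) = 3 fixed-effect degrees of freedom, out of up to 90 × 4 = 360 observations. It needs a change of SAP wording only, with no new data, visits or patients. If the technique effect is constant, the interval is essentially unchanged. The term should be fixed before unblinding.

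### The 0.017 rule protects the 8, 12 and 24 h NRS tests only; opioid use within 4 h, a secondary outcome in the same list, is tested outside it, and Holm would serve better than the fixed threshold

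*Combined protocol and SAP*

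**What the plan says.** All of this is in Section 12.0 of the combined protocol and SAP.

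- **Primary outcome.** There is one, "with the primary outcome being the numeric rate scale (NRS) at 4 hours post-surgery". The sample size is "based on a two-sided two-sample independent t-test with type I error set at 0.05".
- **Secondary outcomes.** The opening paragraph lists them in one sentence: the NRS at 8, 12 and 24 h, and "an indicator of whether woman required opioids (Y/N) within 4 hours of surgery".
- **Multiplicity rule.** Under Statistical Methods: "A p-value of 0.017 will be used to indicate statistical significance in the NRS collected at the three other time points". The stated purpose is "to maintain familywise type I error at .05".
- **Opioid outcome.** Fisher's exact test is assigned to "the dichotomous outcome of whether patients required opioids in the first 4 hours following surgery". No significance level or exploratory status is given.
- **Intervals.** "The mean difference and 95% confidence interval at each time point will be reported".
- **Caution on other outcomes.** The plan advises care with results that can be assessed only in opioid users: "These include the amount of MME in the first four hours and time to first dose". The yes/no outcome is defined for every patient, so this caution does not reach it.

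No sentence makes any secondary test depend on the 4 h result.

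**The concern.** The plan chooses to control familywise error among secondary results, but it divides alpha by three although its own sentence lists four outcomes. A report could then claim an effect on opioid need at an unadjusted 0.05, beside NRS results described as familywise-controlled. Readers would probably credit the whole set with a 5% error rate. Reduced opioid use is part of the trial's hypothesis in Section 1.0, so this claim is likely to be noticed.

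Two smaller matters go with it. A fixed Bonferroni threshold gives up power that a stepwise method would keep. Also, a 95% interval corresponds to a 0.05 test, so a later time point judged at 0.017 can have an interval that excludes zero and still be called non-significant.

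**Working it through.** **Inputs from Section 12.0:** 45 per group; 0.017 for each of three NRS tests; 0.05 for the 4 h test; effect size 0.60. **Assumed, because the documents do not give them:** equal correlation r between NRS times; an opioid test at nominal 0.05 and independent of the NRS tests; two-sided tests with a normal approximation; no missing data.

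1. **The plan's figure.** 0.05/3 = 0.0167, which rounds to 0.017. The upper bound over three tests is 3 × 0.017 = 0.051. If the tests are independent, 1 − (1 − 0.017)³ = 0.0501. Simulation of correlated two-sided tests with no true effect gives about 4.5% at r = 0.5 and 4.0% at r = 0.7. The rule works for the three tests that it names, apart from rounding.

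2. **Adding the opioid test.** If E is the error over the three NRS tests and f the size of the opioid test, the error over all four is 1 − (1 − f)(1 − E).

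| r | E | f = 0.05 | f = 0.03 |
|---|---|---|---|
| 0 | 0.050 | 1 − 0.95 × 0.950 = 9.8% | 1 − 0.97 × 0.950 = 7.9% |
| 0.5 | 0.045 | 1 − 0.95 × 0.955 = 9.3% | 1 − 0.97 × 0.955 = 7.4% |
| 0.7 | 0.040 | 1 − 0.95 × 0.960 = 8.8% | 1 − 0.97 × 0.960 = 6.9% |

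   The second value of f is there because Fisher's test is conservative: its exact size at 45 per arm is 0.020 to 0.030 for opioid rates between 10% and 70%. Independence is not critical. With a correlation of 0.5 between the opioid and 4 h pain statistics (and r = 0.5), simulation gives 9.1% and 7.2%.

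3. **Power under the fixed threshold.** The two-sided critical value for 0.017 is 2.387. For an effect of d SD, power is about Φ(d√(45/2) − 2.387).
   - d = 0.6: Φ(2.846 − 2.387) = Φ(0.459) = 68%.
   - d = 0.4: Φ(1.897 − 2.387) = Φ(−0.490) = 31%.

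4. **Holm over the three NRS times.** The ordered p-values meet 0.05/3, 0.05/2 and 0.05 in turn, stopping at the first failure. The familywise bound stays at 5%, and Holm rejects whenever Bonferroni at 0.05/3 does. With 0.6 SD at all three times and r = 0.5, simulated power per time point rises from 68% to 75%.

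5. **Holm over all four secondary outcomes.** The steps are 0.05/4 = 0.0125, 0.0167, 0.025 and 0.05, so error over the four is at most 5%. With no opioid effect and r = 0.5, simulated power per NRS time is 69% against 68% at 0.6 SD, and within about one point of the current 31% at 0.4 SD.

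6. **Interval mismatch.** The interval that matches 0.017 has 1 − 0.017 = 98.3% coverage. With 0.4 SD at each later time and r = 0.5, there is about a 40% chance under the current plan that at least one later 95% interval excludes zero while its test is called non-significant.

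**The case against.** **The sentence does what it says.** It names three time points, and over those three the error is 5% or less apart from rounding. This stands. A reader might add the 4 h test, or all five tests, and infer that a promised 5% is really about 7% to 13%. At r = 0.5 the four NRS tests do give about 8.5%, and all five about 13.1%. But the documents promise no trial-wide control. Testing a single prespecified primary outcome at 0.05, outside the secondary family, is a common convention and leaves the primary claim at 5%.

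**Bonferroni is a valid method.** This stands too. A reader might infer that it contributes to the excess error. It does not: it is conservative for correlated scores, and its only cost here is power.

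**The missing gate.** A reader might infer that the secondary tests must depend on success at 4 h. Nothing in the documents requires that, and a gate has a real price. With a 4 h gate and Holm over four outcomes (0.6 SD throughout, r = 0.5, no opioid effect), power per later time falls from 68% to 62%. If the 4 h effect is only 0.3 SD and the later effects are 0.6 SD, it falls to 28% even with Holm over just three times. Gating is a trade-off for the team and no part of this point.

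**Unadjusted 95% intervals beside an adjusted threshold are common practice.** Agreed. They need a label, not removal.

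**The size depends on assumptions.** It does, but over r from 0 to 0.7 the four-outcome error stays between about 7% and 10%. None of these objections explains why one of four outcomes in the same list has neither a share of alpha nor an exploratory label.

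**Conclusion.** The point holds in limited form. The 0.017 rule controls familywise error for the 8, 12 and 24 h NRS and leaves out the fourth secondary outcome in Section 12.0's list. The chance of a false claim over those four is about 9% at nominal size, or about 7% with Fisher's true size at 3%, given r = 0.5, an independent opioid test and no true effects.

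The primary conclusion and the sample size are untouched. Separately, the fixed threshold costs about 7 points of power per later time point compared with Holm on the same three tests, at 0.6 SD and r = 0.5. The change is worth making before unblinding; it does not threaten the trial.

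**What to change.** Replace the 0.017 sentence in Section 12.0 with wording such as:

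> The four secondary outcomes (NRS at 8, 12 and 24 h, and opioid use within 4 h) will be tested by the Holm procedure at overall two-sided 0.05. Holm-adjusted p-values will be reported beside the unadjusted 95% confidence intervals, which will be labelled as unadjusted.

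Keep the outcomes named in the sentence. Sections 2.2 and 3.2 give a different secondary list (total opiate consumption, time to first narcotic dose, length of stay) that omits the yes/no outcome, so an unnamed reference to the secondary outcomes would be unclear.

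Alternatively, label the opioid yes/no outcome exploratory and apply Holm to the three NRS times.

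**Cost.** A short wording change, with no extra data or patients. Under the first option the opioid outcome is judged at a stricter level than 0.05 unless the other outcomes have already been rejected. The smallest p-value must pass 0.0125 instead of 0.017, so the chance of at least one claim falls slightly, while average power per NRS time is essentially unchanged. Under the alternative, NRS power rises, but no confirmatory claim can be made on opioid use. Under either option some 95% intervals may still exclude zero without a significance claim; the label tells the reader why.

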1.0 Background & Rationale

First introduced in the 1990's, enhanced recovery after surgery (ERAS) is a multimodal perioperative approach to surgical recovery, shown to lead to early recovery and improved outcomes (1). One of the primary objectives of ERAS programs is appropriate pain control with reduction of postoperative opiate consumption. The mainstay by which most ERAS programs accomplish this goal is an interplay between NSAID's, acetaminophen and local anesthesia. For patients undergoing pelvic organ prolapse repair -following implementation of ERAS programs-it has been shown that patient post discharge recovery is greatly improved and that postoperative opiate consumption is significantly decreased (2,3). In one study of patients undergoing open gynecologic procedures, they were found to have a reduction of mean opioid consumption of 72% with 16% of the patients opioid free prior to discharge (4). Additionally, it has been well documented that patients who undergo gynecologic or pelvic reconstructive surgery are overprescribed opiates at the time of discharge (5). It is recommended that opiate naïve patients be discharged with no more than 15 doses of a given narcotic and that these patients be individualized, as many will require less (5,6).

One of the more controversial and under-investigated aspects of postoperative pain control in the field of Female Pelvic Medicine and Reconstructive Surgery (FPMRS) is the use intraperitoneal local anesthesia.

The two type of peritoneum in the human body are the parietal peritoneum (PP) and visceral peritoneum (VP). The PP is innervated by the somatic nervous system, leading to the perception of localized, sharp pain (7). The VP has sub-mesothelial tissue innervated by the autonomic nervous system, responding to traction, distension and pressure, leading poorly localized, dull pain (7). We also know that the peritoneum is a highly permeable membrane given its long-term use in peritoneal dialysis (8). Due to blockade of free afferent peritoneal nerve endings, it is plausible that intraperitoneal local anesthesia has a role in management of postoperative pain.

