2.0 Objective(s)

- 2.1 Primary Objective
- 2.2 Secondary Objective

2.1: To determine whether intraperitoneal Bupivacaine will decrease pain scores at approximately 4 hours, as determined by a numeric rating scale (NRS) in patients undergoing pelvic organ prolapse repair.

Version Date: 05/25/2023 Page 5 of 13

2.2: Pain scores as determined by NRS at approximately 8, 12 and 24 hours, total opiate consumption postoperatively while inpatient as determined by morphine milligram equivalents (MME), time to first narcotic dose during inpatient stay, and hospital length of stay.

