3.0 Outcome Measures/Endpoints

- 3.1 Primary Outcome Measures
- 3.2 Secondary Outcome Measures
- 3.1: Patient pain will be measured by means of a NRS at 4 hours after surgical pelvic organ prolapse repair.
- 3.2: Patient pain will be measured by means of a NRS at 8, 12 and 24 hours after surgical pelvic organ prolapse repair. Total opiate consumption will be measured in MME, obtained from the electronic medical record. Time to first narcotic dose will be measured in hours and minutes. Hospital length of stay will be measured in days, hours and minutes.

Patients receiving an opioid prescription after short stay surgeries have a 44% increased risk of long term opioid use. The first 4-24 hours postoperatively is the time when these prescriptions are provided. With appropriate control of postoperative pain in the first 4-24 hours, patients may be able to be discharge without opiate prescription.

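### MME and time to first opioid dose are compared only among patients who took opioids, a group that treatment may itself change, so these non-primary comparisons can be attenuated and, in some patterns, reversed

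*Combined protocol and SAP*

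**What the plan says.** Section 12.0 (Statistical Methods) says: "Other outcomes can only be assessed among those that required opioids thus will have lower power". The next sentence is "Thus, caution will be used in interpretation of results", and the outcomes are then named: "These include the amount of MME in the first four hours and time to first dose". For these outcomes the plan fits a linear regression on surgery technique and treatment, giving a mean difference with a 95% confidence interval. If an outcome is non-normal, it uses a generalized linear model to detect the treatment effect. This is inference in a subset, not description.

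One opioid analysis does keep everyone: for "the dichotomous outcome of whether patients required opioids in the first 4 hours following surgery, a Fisher's exact test will be used".

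Elsewhere the same outcomes carry no restriction to users. Section 2.2 lists as secondary "total opiate consumption postoperatively while inpatient as determined by morphine milligram equivalents (MME), time to first narcotic dose during inpatient stay", and section 3.2 says "Total opiate consumption will be measured in MME, obtained from the electronic medical record". The list of secondary outcomes under Sample size/Power in section 12.0 contains the later NRS scores and opioid use yes/no within 4 hours, but neither MME nor time to first dose. The MME window also differs: the inpatient stay in section 2.2, the first four hours in section 12.0.

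**The concern.** Both outcomes exist for every randomised patient. A patient who receives no opioid has consumed 0 MME, and her time to first dose is censored when observation ends. The restriction is therefore a choice.

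The choice matters because the subset forms after treatment. Section 7.0 allows narcotics as needed when pain is poorly controlled, which follows the lavage, and section 1.0 hypothesises lower opiate consumption on bupivacaine. If that hypothesis is true, treatment changes who becomes a user. Patients spared opioids altogether, the clearest successes, leave the bupivacaine side of the comparison, while similar patients on saline stay in. The caution in section 12.0 rests on reduced power and does not mention selection, and cautious reading does not repair a comparison that is no longer randomised.

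At stake is the opioid part of the trial's hypothesis. The Fisher test is a valid all-patient safeguard, but it measures neither amount nor timing.

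**Working it through.** **The plan's own figure.** A two-sided t-test at alpha 0.05, effect size 0.60 and 80% power needs 44.59, so 45 per arm and N = 90 (power 80.4%). This reproduces and is not affected. The plan states no figure for the opioid analyses.

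**Inputs.** 45 per arm (section 12.0). The only opioid-use figure is in section 1.0, for a cited study of open gynecologic surgery: "they were found to have a reduction of mean opioid consumption of 72% with 16% of the patients opioid free prior to discharge". That implies 100 − 16 = 84% use by discharge, in another population. All other use rates and doses below are assumptions. Pairs are saline v bupivacaine.

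**1. MME when every patient's need shifts down.** Let latent need be N(μ, 1) and MME = max(need, 0), in latent SD units, with μ set so that use equals p, that is Φ(μ) = p. Then
- all-patient mean = μp + φ(μ)
- users-only mean = all-patient mean / p

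For 60 v 45% use:
- Saline: μ = 0.2533, φ = 0.3863. All-patient mean 0.152 + 0.386 = 0.538; users 0.538/0.60 = 0.897.
- Bupivacaine: μ = −0.1257, φ = 0.3958. All-patient mean −0.057 + 0.396 = 0.339; users 0.339/0.45 = 0.754.
- All-patient fall: 0.199, or 37%. Users-only fall: 0.143, or 16%.

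The same formula gives the falls below. Power is simulated (4,000 runs) with an assumed technique shift of ±0.3 and adjustment for technique; the Fisher column is exact.

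| Use | Fall, all | Fall, users | Power, users regression | Power, all regression | Power, all stratified Wilcoxon | Power, Fisher any use |
|---|---|---|---|---|---|---|
| 40 v 25% | 48% | 16% | 8% | 34% | 38% | 26% |
| 60 v 45% | 37% | 16% | 13% | 36% | 38% | 22% |
| 60 v 35% | 56% | 25% | 21% | 73% | 78% | 57% |
| 80 v 60% | 44% | 25% | 39% | 76% | 77% | 46% |
| 84 v 70% | 34% | 20% | 32% | 58% | 58% | 26% |
| 84 v 60% | 50% | 30% | 59% | 92% | 93% | 65% |

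The last two rows start from the 84% figure. It describes use by discharge, so they bear on inpatient MME. With discrete 5-MME doses, the first four pairs give falls of 33-52% (all) against 10-17% (users), and power of 37-79% against 7-35%.

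**2. Time to first dose.** Assume exponential times, a 4 h window, 70% saline use and a hazard ratio of 0.5. The hazards are −ln(0.3)/4 = 0.301 and 0.1505 per hour; the undosed shares at 4 h are 0.300 and 0.548.
- Users-only mean, 1/λ − 4e^(−4λ)/(1 − e^(−4λ)): 1.61 h v 1.80 h, difference 0.19 h.
- Restricted mean in all patients, (1 − e^(−4λ))/λ: 2.33 h v 3.01 h, difference 0.68 h.

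The loss depends on how many patients are never dosed while observed. Simulated power, users-only regression against log-rank stratified by technique:

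| Meaning of the use rates | Users-only | All, log-rank |
|---|---|---|
| First four pairs, use by end of observation | 6-12% | 31-69% |
| First four pairs, use by 4 h, all observed to 12 h | 12-53% | 46-90% |
| First four pairs, use by 4 h, all observed to 24 h (82-100% dosed) | 33-78% | 49-92% |
| 84 v 70% by discharge | 11% | 41% |
| 84 v 60% by discharge | 18% | 81% |

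At 24 h the gap within a pair runs from 3 to 39 points.

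**3. When the sign can reverse.** On saline, let 20% take about 5 MME and 40% about 15. All-patient mean = 0.2×5 + 0.4×15 = 7.0; users-only mean = 7.0/0.6 = 11.7. No patient does worse on bupivacaine in any row. Simulated with 5,000 runs and unadjusted t-tests.

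| Pattern on bupivacaine | True all-patient mean | True users mean | Wrong sign, users (significant) | Wrong sign, all |
|---|---|---|---|---|
| Half of light users spared, others 30% less | 4.55 | 9.1 | 4% (0%) | 3% |
| Half spared, others 15% less | 5.53 | 11.05 | 35% (1%) | 16% |
| Half spared, others unchanged | 6.5 | 13.0 | 77% (11%) | 37% |
| All light users spared, others 15% less | 5.1 | 12.75 | 75% (8%) | 11% |
| All light users spared, others unchanged | 6.0 | 15.0 | 97% (43%) | 27% |

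Only the last three rows reverse the true direction (users mean above 11.7).

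**4. No treatment effect.** The users-only tests reject in 4-6% of simulated trials, so false positives are not the problem.

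**The case against.** - **Scale.** The plan's linear model estimates a mean difference, and percentage falls make the loss look larger. This is fair. In the continuous model the users-only difference keeps about 71-85% of the all-patient difference (0.143/0.199 = 72% for 60 v 45%); with discrete doses it keeps 53-59%. With 30% saline use and a shift of 0.6 latent SD there is no absolute attenuation: −1.33 among users against −1.25 in all patients (latent SD 10). Attenuation is common, not universal.
- **Power is already disclosed.** The plan admits lower power, and the power gaps above mix the smaller sample with selection without separating them. True, but the admission does not cover the loss of the randomised comparison.
- **Reversal is a corner case.** It needs light users to be spared while heavier users change little, and it does not arise in the uniform-shift model. That stands.
- **The numbers are not this trial's.** The 84% figure comes from other surgery, and its comparators are assumed. So no size of bias can be stated for this trial; the logic does not depend on one.
- **The safeguards help.** Fisher's test plus amount among users are the two parts of a two-part model. But the plan never combines them into an all-patient difference, and Fisher's test alone has 22-57% power in the first four pairs.
- **The inconsistencies are separate.** The conflicts over window and status would exist anyway and add no weight to the selection argument. They must still be settled before an all-patient analysis can be written.

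**Conclusion.** The concern holds. Section 12.0 estimates treatment effects in a subset formed after treatment, on the mistaken premise that non-users cannot be analysed. If bupivacaine changes who needs opioids, the users-only contrasts do not estimate its effect on consumption or on time to first dose.

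The size depends on assumed use rates. For MME, the all-patient fall is 37-56% against 16-25% among users over the four main pairs, with a milder loss on the absolute scale. For time to first dose, the loss is large if many patients are never dosed while observed, and can be small if nearly all are. Reversal is possible but not expected.

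The primary NRS analysis and N = 90 are untouched, and type I error under no effect stays near 5%. The point should be fixed because it governs what the trial can say about opioid consumption, which is part of its hypothesis.

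**What to change.** 1. Reconcile the MME window (inpatient total in section 2.2, first four hours in section 12.0) and the status of both outcomes (secondary in sections 2.2 and 3.2, absent from the secondary list in section 12.0).
2. Analyse MME in all randomised patients, with 0 for non-users, and report an overall difference that accounts for technique. Examples are a stratified Wilcoxon test with a mean difference and bootstrap 95% CI, or a two-part model combined into one mean difference.
3. Analyse time to first dose in all randomised patients as censored data: Kaplan-Meier with a log-rank test or Cox model stratified by technique. Prespecify a censoring time consistent with the inpatient definition in section 2.2, and report how many patients leave before it. State that censoring at discharge may be informative, because discharge may depend on pain, and that a short fixed window would narrow the section 2.2 endpoint.
4. Keep users-only summaries as description, without a treatment-effect test, and keep the Fisher test.

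**Cost.** Three decisions (MME window, outcome status, censoring time), revised SAP wording and a few lines of code. MME, dose times and length of stay already come from the hospital record, so no new data or patients are needed. Two downsides remain: the MME effect is on a scale that includes zeros, and same-day discharges are observed for less time whichever analysis is used.
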